10.4 Vital Signs

The observed value and changes from baseline of blood pressure, heart rate, and temperature will be summarized by dose level and dose schedule (if applicable) and by visit for Safety Population.

10.5 12-lead ECG

Descriptive statistics of actual value and change from baseline for ECG parameters including heart rate, PR interval, QRS interval, QT interval, QTc interval, and QTcF interval (Fridericia's corrections) will be presented for baseline visit and scheduled post-treatment visit. The average of triplicate 12-lead ECG results at each timepoint will be used for descriptive statistics. Standard and triplicate 12-lead ECG data will be listed for each participant and time point for the Safety population.

Overall ECG interpretation category (normal, abnormal NCS [not clinically significant], abnormal CS [clinically significant], and not evaluable) is collected in the CRF at baseline and each scheduled post-baseline visit. Shifts tables (shift from baseline to the worst post-baseline values during the treatment emergent period) will be presented.

The QTcF will be categorized into the following categories to identify potentially clinically important changes:

- QTc interval >450 msec and ≤ 480 msec

- QTc interval >480 msec and ≤ 500 msec
- QTc interval >500 msec

The change from baseline in QTcF will also be categorized separately as follows:

- QTc interval increases from baseline by >30 msec and ≤ 60 msec
- QTc interval increases from baseline by >60 msec

For the number of subjects meeting each category for the post-baseline results, the numerator is the number of subjects with meeting the criterion at post-baseline and the denominator is the number of subjects with normal baseline and at least one post baseline assessment in the Safety Population. For the number of subjects meeting each category for the change from baseline, the numerator is the number of subjects with meeting the criterion at post-baseline and the denominator is the number of subjects with baseline and at least one post baseline assessment in the Safety Population.

All ECG tables and listings will be reported on the Safety Population.

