6. Active, uncontrolled bacterial, fungal, or viral infection, including hepatitis B virus (HBV), hepatitis C virus (HCV), known human immunodeficiency virus (HIV), or acquired immunodeficiency syndrome (AIDS)-related illness. In equivocal cases, participants with a negative viral load may be eligible. Eligibility criteria for HIV positive participants currently on highly active antiretroviral therapy should be evaluated and discussed with the Medical Monitor and will be based on current and past CD4 and T cell counts, history (if any) of AIDS-defining conditions (e.g., opportunistic infections), and status of HIV treatment. Participants with previously treated HBV and HCV with negative viral load are eligible.
7. Clinically significant vascular (both arterial and venous) and nonvascular cardiac conditions, active or within 6 months prior to enrollment, including:
 - a. Arterial disease such as cerebral vascular accident/stroke (including transient ischemic attack), myocardial infarction, and unstable angina
 - b. Venous diseases such as deep vein thrombosis and/or pulmonary embolism, central venous thrombosis (active or within 3 months prior to enrollment)
 - c. Nonvascular cardiac disease such as congestive heart failure (New York Heart Association Classification Class ≥ 2)
 - d. Conduction abnormality not controlled with pacemaker or medication
 - e. Significant ventricular or supraventricular arrhythmias, including history of Torsades de pointes (TdP) unless all risk factors that contributed to TdP have been corrected. Participants with chronic rate-controlled atrial fibrillation/flutter in the absence of other cardiac abnormalities are eligible.
 - f. Family history of sudden unexplained death or long electrocardiogram (ECG) interval measured from the onset of the QRS complex to the end of the T wave (QT syndrome)
 - g. History of risk factors for QT prolongation or TdP (e.g., organic heart disease, congestive heart failure, hypokalemia, hypocalcemia, hypomagnesemia, congenital long QT syndrome, myocardial ischemia, or infarction)
8. Mean resting QT interval corrected for heart rate (QTc) using the Fridericia formula (QTcF) >470 msec (as calculated per institutional standards) demonstrated by at least 2 ECGs ≥ 1 minute apart at trial entry

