5. DEFINITIONS AND CONVENTIONS FOR DATA HANDLING

All analyses will be performed using SAS® Version 9.4 or higher.

Unless specified otherwise, the analyses of data collected will be descriptive and summaries will be presented separately for each dose level, dose schedule (if applicable) and in total for the specified analysis population. Statistical analysis will be purely descriptive and no formal hypothesis testing or comparative analysis between dose level will be performed. Confidence intervals (CIs) will be constructed at two-side 95% level where appropriate.

Frequency distributions for categorical variables will be provided as the number of subjects in the category and the percentages of the total number of subjects in the given population as noted. Percentages will be reported to one decimal place.

The descriptive statistics for continuous variables will be the number of subjects, mean, standard deviation, median, lower and upper quartile, minimum and maximum. Mean, median will be reported to 1 decimal place, while the standard deviation will be reported to 2 decimal places. Minimum and maximum will be reported the same as the original data.

Summary tables may be replaced with listings when appropriate. For instance, an AE Frequency table may be replaced with a listing if it only contains a few unique PTs reported on relatively few subjects.

All tables will be summarized by treatment regimen (Arm 1 and Arm 2 respectively), dose level, and dose schedule, and include an overall column for Arm 1 and Arm 2 respectively unless otherwise specified.

All listings will be sorted by arm, dose level, and dose schedule if applicable, subject ID and, if applicable, by visit date unless otherwise specified in the text.

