10.1 Dose Limiting Toxicities (DLT)

The number of DLTs will be summarized by treatment arms for the DLT Evaluable Population. A toxicity will be considered a DLT if it occurs from the first dose to the end of Cycle 1 [REDACTED]
[REDACTED], meets the pre-defined criteria for DLTs, is deemed at least possibly related to trial treatment, and is not clearly and incontrovertibly due to disease progression or extraneous cause. Toxicity will be assessed using CTCAE v5.0, unless other specified. Details of DLTs will be listed.

DLTs will be defined as any of the following:

- Any death not clearly due to the underlying disease or extraneous causes

Hematologic TEAEs:

- Grade 4 neutropenia
- Febrile neutropenia (defined as absolute neutrophil count (ANC) <1000 cells/ μ L with a single temperature of 38.3°C [100.4°F] for > 1 hour).
- Grade 4 thrombocytopenia or Grade 3 thrombocytopenia associated with Grade \geq 2 bleeding.
- Grade 4 anemia or Grade 3 anemia requiring red blood cell (RBC) transfusion given to participants with documented anemia-related symptoms.

Non-Hematologic TEAEs:

- Any Grade \geq 3 TEAE except the below
 1. Grade \geq 3 non-hematologic laboratory abnormalities that are asymptomatic and respond to medical intervention or resolve to grade 1 in \leq 72 hours.
 2. Grade 3 fatigue with duration < 7 days
 3. Grade \geq 3 nausea/vomiting/diarrhea that lasts \leq 72 hours and resolves with or without optimal supportive care.
 4. Grade \geq 3 amylase or lipase elevation not associated with symptoms or clinical manifestations of pancreatitis.
 5. The use of red blood cell transfusion for anemia Grade <3 or the use of G-CSF for Grade <4 neutropenia
- Symptomatic Grade \geq 3 QTc prolongation (QTcF \geq 501 msec on at least two separate ECGs), or asymptomatic Grade \geq 3 QTc prolongation that has been confirmed by repeat testing and reevaluation by a qualified person and persists after correction of reversible causes such as electrolyte abnormalities or hypoxia.
- Drug-induced liver injury meeting Hy's Law criteria defined as:
 1. ALT or AST \geq 3-fold above the Upper Limit of Normal (ULN) or \geq 5.0 x ULN in the case of liver metastases at baseline and
 2. Serum total bilirubin \geq 2-fold above ULN (without findings of cholestasis) and

3. Alkaline phosphatase < 2 x ULN and
4. No other overt reason for liver injury

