- k. **ECG:** 12-lead ECGs to be done in triplicate \geq 1 minute apart per Table 3 and Table 4 in the study protocol. Participants should be in supine position and resting for at least 10 minutes before trial-related ECGs. The ECG assessment on C1D1 is for Arm 2 only. For additional cycles, ECG is only to be performed pre-dose on C2D1 and C4D1 and if clinically indicated.
- l. **Pregnancy Test:** For WOCBP, a serum pregnancy test is required at Screening. If pregnancy test was done within 48 hours of Day-2, repeat testing is not required. A serum or urine pregnancy test must be performed on Day 1 of each cycle, at EOT, and at Safety Follow-up. Pregnancy test can be performed more frequently if required per local regulations.
- m. **Safety Laboratory Tests:** Clinical laboratory tests (including serum or plasma chemistry, hematology, and urinalysis) will be performed at local laboratories according to the laboratory's normal procedures. See protocol Section 8.3.4 for a complete listing of laboratory tests to be performed.
- n. **Serum Testosterone:** Required only for participants with prostate cancer without history of bilateral orchiectomy. These participants must have serum testosterone $<$ 50 ng/dL documented during Screening.
- o. **Serum Tumor Markers:** This assessment applies only to participants with cancers being monitored by circulating tumor markers (e.g., CA-125 or PSA). The screening assessment may be used as the Day -2 assessment as long as this assessment is within 96 hours of C1D1. For participants in Arm 2 the Day -2 assessment may be performed at any date within 96 hours of the dose on C1D1 (as long as it is pre-dose on C1D1).
- p. **ctDNA Whole Blood:** The Day -2 collection is for participants enrolled in Arm 1 and the C1D1 collection is for participants enrolled in Arm 2. Blood can be collected either pre- or post-dose for all timepoints except for on Day -2 (Arm 1) or C1D1 (Arm 2), which should be collected pre-dose.
- q. **Mandatory Archival Tumor Tissue:** Archival tissue (primary tumor preferred) should be submitted to the Sponsor-designated laboratory during Screening or by C1D1 (+7 days). Refer to Laboratory Manual for further details. If archival tissue does not meet Laboratory Manual specifications, a fresh biopsy can be provided in place of archival tissue. If adequate archived tumor tissue is not available and/or a fresh biopsy cannot be safely performed, the participant may still be eligible with prior Sponsor approval.

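### The absolute QTcF categories in SAP 10.5 put an unrestricted numerator over an undefined normal-baseline denominator, although entry allows QTcF up to 470 msec

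*SAP*

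**What the plan says.** SAP 10.5 (12-lead ECG) sets three absolute QTcF categories: >450 to 480, >480 to 500 and >500 msec. For these rows, "the numerator is the number of subjects with meeting the criterion at post-baseline". No baseline condition is attached to that count. The group it is divided by is narrower: "the denominator is the number of subjects with normal baseline and at least one post baseline assessment in the Safety Population".

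The change-from-baseline rows (>30 to 60 msec and >60 msec) are built differently. There, "the denominator is the number of subjects with baseline and at least one post baseline assessment in the Safety Population", without the word normal. The restriction therefore applies to the absolute rows only.

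Neither SAP 10.5 nor the baseline definition in SAP 5.1 gives a msec value for normal. The only other use of the word in SAP 10.5 is a CRF item: "Overall ECG interpretation category (normal, abnormal NCS [not clinically significant], abnormal CS [clinically significant], and not evaluable". That is a reading of the whole tracing, not a QTcF value, and the text does not link it to this denominator.

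In Protocol 1.1, the words "QTcF) >470 msec (as calculated per institutional standards" in exclusion criterion 8 set the QTcF limit at entry. A value of 470 msec or less is admissible.

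**The concern.** The entry limit lies inside the SAP's first category. A participant with a baseline of 451–470 msec meets the >450–480 criterion before the first dose and, if normal means ≤450 msec, is outside the denominator. The text then allows two tables from the same data:

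- **Literal:** the participant counts in the numerator but not in the denominator. The result is not a proportion of any defined group, and an unchanged value counts as an event.
- **Restricted:** the numerator is limited to the denominator's participants. The >450–480 row is then a valid new-onset rate, but someone who enters at 465 msec and reaches 505 msec is missing from the >500 row, the row that matters most.

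Reading normal differently does not solve it. With ≤470 msec the fraction is valid, but an unchanged 460 msec still counts as an event. With the CRF interpretation, membership can turn on findings unrelated to QTcF; exclusion 7e, for example, admits chronic rate-controlled atrial fibrillation.

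The effect on a percentage can be large because denominators are small: "All tables will be summarized by treatment regimen (Arm 1 and Arm 2 respectively), dose level, and dose schedule".

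**Working it through.** The plan states no percentage here, so there is no figure to reproduce. The calculations below are illustrations.

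**Inputs from the documents:** category bounds (SAP 10.5); entry limit of 470 msec (Protocol 1.1, exclusion 8); initial cohorts of up to 3 in Arm 1 and 3 in Arm 2 (Protocol 1.1); possible expansion of an Arm 2 level to at least 6 (Protocol 1.1, SAP 2.1); about 12 participants in Arm 1 (SAP 2.3).

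**Assumptions:** normal means ≤450 msec; the frequency *p* of a 451–470 msec baseline, which the documents do not give, is varied from 2% to 20%.

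**1. One participant unchanged at 451–470 msec, nobody newly prolonged.** The literal >450–480 row is 1/(n − 1). The rate among those at risk is 0/(n − 1) = 0%.

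- n = 3: 1/2 = 50%
- n = 6: 1/5 = 20%
- n = 12: 1/11 = 9.1%

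**2. A worked level of six.** Baselines are 430, 430, 430, 430, 460 and 465 msec; worst post-baseline values are 440, 440, 440, 465, 460 and 505 msec. Four baselines are ≤450 msec. The at-risk column takes participants whose baseline is at or below the row's lower bound.

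| Row (msec) | Literal | Restricted to ≤450 | Normal read as ≤470 | At risk for that row |
|---|---|---|---|---|
| >450–480 | 2/4 = 50% | 1/4 = 25% | 2/6 = 33.3% | 1/4 = 25% |
| >480–500 | 0/4 | 0/4 | 0/6 | 0/6 |
| >500 | 1/4 = 25% | 0/4 = 0% | 1/6 = 16.7% | 1/6 = 16.7% |

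The restricted reading is right in the first row and wrong in the last. The ≤470 reading is the reverse. The literal reading is wrong in both.

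**3. How often could it arise?** The chance of at least one 451–470 msec baseline is 1 − (1 − p)^n.

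| p | n = 3 | n = 6 |
|---|---|---|
| 2% | 5.9% | 11.4% |
| 5% | 14.3% | 26.5% |
| 10% | 27.1% | 46.9% |
| 20% | 48.8% | 73.8% |

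**4. Could a literal rate exceed 100% or be undefined?** With no drug effect and k such participants, this needs k > n − k, where k is Binomial(n, p). Over p = 2% to 20% the probability is 0.1% to 10.4% at n = 3 and at most 1.7% at n = 6. It is possible but unlikely.

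**The case against.** The best defence is the SAP's general convention. Section 5 expresses category counts as percentages of the stated population, and SAP 10.5 states that population. On that basis a programmer would draw the numerator from the denominator, and ≤450 msec is the natural complement of the lowest category. This is a fair reading, and it removes the 50%, 20% and 9.1% figures. It does not remove the second problem: under it the 465 to 505 msec participant is still absent from the >500 row.

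The size can also be disputed:

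- The tables include an overall column per arm. If Arm 2 reaches about 24 in escalation plus 16 backfill participants, one unchanged participant moves the literal rate only to 1/39 = 2.6%.
- The six-participant example needs two baselines of 451–470 msec. Over the same 2% to 20% range that has probability 0.6% to 34% at n = 6, before allowing for a >500 msec event.
- The range for *p* is assumed, and the exclusions for QT risk factors and QT-prolonging drugs may make such baselines uncommon.

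These points limit how often and how much the table goes wrong. They do not make the definition correct.

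Other outputs give partial cover. The 465 to 505 msec case is a rise of 40 msec, so it appears in the >30 to 60 change row and in the ECG listings. If reported as an adverse event it would also enter the TEAE summaries (SAP 10.2). The DLT listing covers less: "A toxicity will be considered a DLT if it occurs from the first dose to the end of Cycle 1", whereas ECGs go on later: "For additional cycles, ECG is only to be performed pre-dose on C2D1 and C4D1 and if clinically indicated". The ECG shift table uses the overall interpretation category. None of these corrects the >500 row.

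**Conclusion.** The concern holds. For the three absolute QTcF rows, SAP 10.5 gives a numerator without a stated baseline condition and a denominator resting on an undefined term, while entry admits values inside the first category. None of the readings examined (literal, restricted to ≤450 msec, or normal as ≤470 msec) gives a sound result in both the >450–480 and the >500 rows.

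If normal means ≤450 msec, one unchanged participant can produce a spurious 50% at a level of three or 20% at a level of six. In the worked level of six, the >500 row ranges from 0% to 25% against 16.7% among those at risk. The error arises only if a participant with a non-normal baseline meets a category, and the documents do not show how likely that is.

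The consequence is limited. The table is descriptive, BOIN decisions use DLT counts, and the change-from-baseline rows are unaffected. It should still be corrected: it is a safety table in a trial whose primary objective is safety, and the correction is cheap.

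**What to change.** Use the same participants in numerator and denominator, and define them in msec for each row:

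- **Denominator:** participants with a post-baseline QTcF whose baseline QTcF is at or below the row's lower bound (≤450 for >450–480, ≤480 for >480–500, ≤500 for >500).
- **Numerator:** those in that denominator whose worst post-baseline QTcF falls in the category.

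Participants entering at 451–470 msec then count in the two higher rows and neither inflate nor dilute the first. Given the entry limit, the two higher rows will normally share one denominator.

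Alternatively, replace the rows with a shift table of baseline by worst post-baseline QTcF category (≤450, >450–480, >480–500, >500 msec) for everyone with both values. SAP 10.3 already uses this format for laboratory grades.

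The cost is one or two SAP sentences and one derivation. With the first option, denominators differ by row and must be printed. No new data are needed.

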10.6 Performance Status

ECOG score will be presented in listings.

11. INTERIM ANALYSIS

Due to the exploratory nature of this Phase 1 trial, data will be assessed descriptively on an ongoing basis after each dose cohort based on safety and clinical activity information to inform the dose selection. No formal statistical inference will be made to these interim evaluations.

12. APPENDIX

Table 5 Schedule of Activities (Arms 1 and 2)

	Pre-screening	Screening ^a			Cycle 1						Additional Cycles		EOT Visit ^b	Safety Follow-up ^c	Long-term Follow-up ^d	
					1	2 (Arm 2 only)	8 (+2) ^e	9 ^e	15 (+2) (Arm 2 only)	17 (+2) (Arm 1 only)	1 (-2/+3) ^f	8 (+2) ^g				
Trial Days	-180 to -3	-30 to -3			1											
Procedures/Assessments																
Pre-screen informed consent	X															
Screening/main informed consent		X														
Inclusion/exclusion criteria		X														

	Pre-screening	Screening ^a	Cycle 1								Additional Cycles		EOT Visit ^b	Safety Follow-up ^c	Long-term Follow-up ^d
Trial Days Procedures/ Assessments	-180 to -3	-30 to -3	■	■	1	2 (Arm 2 only)	8 (+2) ^e	9 ^e	15 (+2)	17 (+2) (Arm 1 only)	1 (-2/ +3) ^f	8 (+2) ^g	Within +7 days of Disc of Trt date	30 days (+14) after last dose	Up to 24 months after Disc of Trt date
Molecular eligibility ^h	X ^h														
Demographics	X														
Medical/cancer history		X													
Physical examination		X										X			
Abbreviated PE			■								X ⁱ			X	
Height		X													
Weight		X	■								X		X	X	
Vital sign measurements ^j		X	■		X		X		X	X	X	X ^g	X	X	
ECOG performance status			X	■							X		X	X	
12-lead ECG ^k		X	■		X ^k		X				X ^k				
Pregnancy test ^l		X	■								X		X	X	
Chemistry laboratory tests and urinalysis ^m			X	■							X		X	X	
Hematology tests ^m		X	■				X		X	X	X	X ^g	X	X	
Serum testosterone ⁿ			X ⁿ												
Serum tumor markers ^o		X	■							X			X		
ctDNA whole blood ^p		X	■		X ^p					X			X		
Archival tumor tissue ^q			X ^q												
Paired tumor biopsies (Arm 1 only) ^r			X ^r							X ^r					

	Pre-screening	Screening ^a	Cycle 1								Additional Cycles		EOT Visit ^b	Safety Follow-up ^c	Long-term Follow-up ^d
Trial Days Procedures/ Assessments	-180 to -3	-30 to -3	■	■	1	2 (Arm 2 only)	8 (+2) ^e	9 ^e	15 (+2)	17 (+2) (Arm 1 only)	1 (-2/ +3) ^f	8 (+2) ^g	Within +7 days of Disc of Trt date	30 days (+14) after last dose	Up to 24 months after Disc of Trt date
Progression Tumor biopsy (optional) ^s													X ^s		
			■	■	■	■	■	■	■	■					
Tumor assessments ^w		X ^x		To be assessed every 6 weeks (± 7 days) from Cycle 1 Day 1. After the first 3 tumor assessments (~5 months/22 weeks on treatment) assessments will be every 9 weeks (± 7 days).											
RP-3467 administration ^y			■	See Protocol Section 6.2, Dosage and Administration											
Olaparib administration ^y				See Protocol Section 6.2, Dosage and Administration											
Review of dosing diary ^z				X		X		X	X	X		X			
AE assessment			During Screening, only AEs considered related to trial procedures or SAEs need to be reported. Following initiation of dosing AE to be collected through 30 days after the last dose of trial intervention or start of new anticancer therapy, whichever is earlier. SAEs believed to be due to trial treatment should be reported through the end of trial date or whenever the Investigator becomes aware thereafter.												
Concomitant medications/procedures			To be collected from the time of Screening visit through the Safety Follow-up visit												
Transfusion and growth factors			If administered, to be collected from the time of Screening visit through the Safety Follow-up visit												
Post-trial therapy data collection															X
Survival status															X
Secondary hematologic malignancy status															X

AE = adverse event; BID = twice daily; CA-125 = cancer antigen 15, CT = computed tomography; ctDNA = circulating tumor DNA; CXDX = Cycle X Day X, Disc of Trt = Discontinuation of treatment; ECG = electrocardiogram; ECOG = Eastern Cooperative Oncology Group; EOT = end of treatment; ICF = informed consent form; MRI = magnetic resonance imaging; NGS = next-generation sequencing; PCWG3 = Prostate Cancer Working Group 3; PE = physical examination; PK = pharmacokinetic; PSA = prostate-specific antigen; RECIST = Response Evaluation Criteria in Solid Tumors; SAE = serious adverse event;

WOCBP = women of childbearing potential

a. **Screening:** Screening Period extends from Day -30 to Day -3. Screening laboratory assessments (hematology, chemistry, urinalysis, and serum tumor marker) may be used as Day -2 assessments if performed within 48 hours of the first dose of trial intervention. ECOG performance status and PE that are completed within 24 hours of first dose of trial treatment may be used as Day -2 assessments. Procedures that are to be performed as part of the practice of medicine and which would be done whether or not trial

entry was contemplated, such as for diagnosis or treatment of a disease or medical condition, may be performed and the results subsequently used for determining trial eligibility without first obtaining consent. Participants must continue to meet eligibility criteria prior to the first dose of RP-3467 on Day -2.

- b. **EOT Visit:** An End-of-Treatment visit will be conducted following the last dose of trial intervention and within +7 days of the discontinuation of treatment date. If a participant comes to the clinic to start a new cycle but the decision is made to discontinue treatment, that visit may be used as the EOT visit. The EOT visit should occur prior to the start of subsequent anticancer treatment.
- c. **Safety Follow-up:** Required for all participants who discontinued from treatment for whatever reason. The window for the Safety Follow-up visit will be 30 (+14) days from the last dose of trial intervention.
- d. **Long-Term Follow-Up:** Follow-up will be conducted at approximately 3, 6, 12, 18, and 24 months (\pm 14 days) after the discontinuation of treatment date. This follow-up will be conducted by telephone contact or standard method used by participating centers and agreed by the Sponsor. This does not require an in-person visit. Information regarding post-trial therapy, survival status, and hematologic malignancy diagnosis will be collected. The Long-term follow-up period may end sooner if a participant is diagnosed with a hematologic malignancy or if death is known to have occurred prior to 24 months.
- e. **C1D8 and C1D9:** A +2 day window is allowed for the C1D8 visit. If a window is used for C1D8, the same window should be used for C1D9.
- f. **CXD1:** The start of a new additional cycle should always coincide with the start of trial intervention administration for that cycle. A +3-day window is allowed for the start of new cycles, though cycles should never start early and should be at least 21 days in length. A -2 day window is allowed for the safety assessments scheduled for the CXD1 visit to enable flexibility with visit scheduling.
- g. **CXD8:** Hematology and vital signs to be assessed only on Cycles 2 and 3.
- h. **Molecular Eligibility:** NGS reports will be emailed to the Sponsor-approved central annotation group for central review to confirm molecular eligibility.
- i. **Abbreviated PE:** Starting at Cycle 2, abbreviated PE to be performed every 2 cycles (unless full PE necessary by Investigator judgment).
- j. **Vital Signs:** Blood pressure, heart rate, and temperature to be measured after the participant has been sitting for 5 minutes.
- k. **ECG:** 12-lead ECGs to be done in triplicate \geq 1 minute apart per Table 3 and Table 4 in the study protocol. Participants should be in supine position and resting for at least 10 minutes before trial-related ECGs. The ECG assessment on C1D1 is for Arm 2 only. For additional cycles, ECG is only to be performed pre-dose on C2D1 and C4D1 and if clinically indicated.
- l. **Pregnancy Test:** For WOCBP, a serum pregnancy test is required at Screening. If pregnancy test was done within 48 hours of Day-2, repeat testing is not required. A serum or urine pregnancy test must be performed on Day 1 of each cycle, at EOT, and at Safety Follow-up. Pregnancy test can be performed more frequently if required per local regulations.
- m. **Safety Laboratory Tests:** Clinical laboratory tests (including serum or plasma chemistry, hematology, and urinalysis) will be performed at local laboratories according to the laboratory's normal procedures. See protocol Section 8.3.4 for a complete listing of laboratory tests to be performed.
- n. **Serum Testosterone:** Required only for participants with prostate cancer without history of bilateral orchiectomy. These participants must have serum testosterone $<$ 50 ng/dL documented during Screening.
- o. **Serum Tumor Markers:** This assessment applies only to participants with cancers being monitored by circulating tumor markers (e.g., CA-125 or PSA). The screening assessment may be used as the Day -2 assessment as long as this assessment is within 96 hours of C1D1. For participants in Arm 2 the Day -2 assessment may be performed at any date within 96 hours of the dose on C1D1 (as long as it is pre-dose on C1D1).
- p. **ctDNA Whole Blood:** The Day -2 collection is for participants enrolled in Arm 1 and the C1D1 collection is for participants enrolled in Arm 2. Blood can be collected either pre- or post-dose for all timepoints except for on Day -2 (Arm 1) or C1D1 (Arm 2), which should be collected pre-dose.
- q. **Mandatory Archival Tumor Tissue:** Archival tissue (primary tumor preferred) should be submitted to the Sponsor-designated laboratory during Screening or by C1D1 (+7 days). Refer to Laboratory Manual for further details. If archival tissue does not meet Laboratory Manual specifications, a fresh biopsy can be provided in place of archival tissue. If adequate archived tumor tissue is not available and/or a fresh biopsy cannot be safely performed, the participant may still be eligible with prior Sponsor approval.
- r. **Paired Biopsies (Arm 1 Only):** Tumor biopsies will be collected during Screening and on C1D17 (+2 days) 1-4 hours post-dose. Participants must have had a minimum of 3 consecutive days of dosing with trial intervention prior to the on-treatment biopsy collection. If biopsy collection at this timepoint is not possible, the Sponsor should be contacted to get approval for collection on an alternative day. Once approved, the participant should have the biopsy as soon as possible after the participant has received at least 3 consecutive days of trial intervention.
- s. **Optional Post-Progression Tumor Biopsy:** An optional tumor biopsy will be requested post-progression for participants with prior confirmed responses or prolonged stable disease to evaluate mechanisms of resistance.
- w. **Tumor Assessment:** Tumor assessments by disease-appropriate standard criteria (RECIST v1.1) using CT/MRI with contrast of known sites of disease as clinically indicated. A baseline tumor assessment must be performed within 28 days of the first dose. Subsequent assessments must be performed every 6 weeks (\pm 7 days) from C1D1 for the first 3 assessments (~5 months/22 weeks on-treatment), or sooner if clinically indicated. Thereafter, assessments must be performed every 9 weeks (\pm 7 days). Per RECIST v1.1, complete response or partial response should be confirmed; tumor imaging for confirmation of response must be performed at least 4 weeks after the first indication of response. The subsequent tumor imaging after the confirmation of response should be obtained per the original scheduled interval from the confirmatory scan (6 weeks \pm 7 days during the first ~5 months of trial treatment or every 9 weeks thereafter). For participants with prostate cancer, radionuclide bone scans will be required at baseline and on the same schedule as the RECIST assessments for the assessment of bone disease per PCWG3 criteria. The appearance of new lesions on a bone scan should be confirmed on a subsequent bone scan before determining disease progression based on these results. If a participant

discontinues treatment for a reason other than disease progression, withdrawal of consent to trial, lost to follow-up, or death, the date that radiographic disease progression is next confirmed should be documented if prior to the start of the subsequent anticancer treatment. All radiographic images/scans at the timepoints specified as well as any unscheduled images/scans should be archived by the trial sites for potential future evaluation.

- x. **Tumor Assessment at Screening:** Scans performed prior to signing of the ICF as part of routine clinical management are acceptable for use as baseline tumor imaging if they are of diagnostic quality and performed within 28 days prior to the first dose.
- y. **RP-3467 and Olaparib Administration:** The [REDACTED] RP-3467 dose should start on a Monday or Tuesday, if unable to accommodate weekend visits.
- z. **Review of Dosing Diary:** Dosing diary will be reviewed at each participant visit and collected at each CXD1 visit and at EOT. Additional details are in the Pharmacy Manual.

Table 6 Schedule of Activities (Arm 2 [REDACTED])

	Pre-screening	Screening ^a	Cycle 1						Additional Cycles		EOT Visit ^b	Safety Follow-up ^c	Long-term Follow-up ^d
Trial Days	-180 to -3	-30 to -3	1	2 (Arm 2 only)	8 (+2) ^e	9 ^e	15 (+2)	17 (+2) (Arm 2 only)	1 (-2/ +3) ^f	8 (+2) ^g	Within +7 days of Disc of Trt date	30 days (+14) after last dose	Up to 24 months after Disc of Trt date
Procedures/ Assessments													
Pre-screen informed consent	X												
Screening/main informed consent		X											
Inclusion/exclusion criteria		X											
Molecular eligibility ^h	X ^h												
Demographics	X												
Medical/cancer history		X											
Physical examination		X									X		
Abbreviated PE									X ⁱ			X	
Height		X											
Weight		X							X		X	X	
Vital sign measurements ^j		X	X		X		X	X	X	X ^g	X	X	
ECOG performance status		X							X		X	X	
12-lead ECG ^k		X	X ^k		X				X ^k				

[figure not shown]
	Pre-screening	Screening ^a	Cycle 1						Additional Cycles		EOT Visit ^b	Safety Follow-up ^c	Long-term Follow-up ^d
Trial Days Procedures/ Assessments	-180 to -3	-30 to -3	1	2 (Arm 2 only)	8 (+2) ^e	9 ^e	15 (+2)	17 (Arm 1 only)	1 (-2/ +3) ^f	8 (+2) ^g	Within +7 days of Disc of Trt date	30 days (+14) after last dose	Up to 24 months after Disc of Trt date
Pregnancy test ^h		X							X		X	X	
Chemistry laboratory tests and urinalysis ^m		X							X		X	X	
Hematology tests ^m		X			X		X	X	X	X ^g	X	X	
Serum testosterone ⁿ		X ⁿ											
Serum tumor markers ^o		X							X		X		
ctDNA whole blood ^p		X	X ^p						X		X		
Archival tumor tissue ^q		X ^q											
Paired tumor biopsies (Arm 1 only) ^r		X ^r						X ^r					
Progression Tumor biopsy (optional) ^s											X ^s		
[REDACTED]			■	■	■	■		■	■				
Tumor assessments ^w		X ^w	To be assessed every 6 weeks (± 7 days) from Cycle 1 Day 1. After the first 3 tumor assessments (~5 months/22 weeks on treatment) assessments will be every 9 weeks (± 7 days).										
RP-3467 administration ^y			See Protocol Section 6.2, Dosage and Administration										
Olaparib administration ^y			See Protocol Section 6.2, Dosage and Administration										
Review of dosing diary ^z			X		X		X	X	X		X		
AE assessment		During Screening, only AEs considered related to trial procedures or SAEs need to be reported. Following initiation of dosing AE to be collected through 30 days after the last dose of trial intervention or start of new anticancer therapy, whichever is earlier. SAEs believed to be due to trial treatment should be reported through the end of trial date or whenever the Investigator becomes aware thereafter.											

[figure not shown]
	Pre-screening	Screening ^a	Cycle 1						Additional Cycles		EOT Visit ^b	Safety Follow-up ^c	Long-term Follow-up ^d
Trial Days Procedures/ Assessments	-180 to -3	-30 to -3	1	2 (Arm 2 only)	8 (+2) ^e	9 ^e	15 (+2)	17 (Arm 2 only)	1 (-2/)	8 (+2) ^g	Within +7 days of Disc of Trt date	30 days (+14) after last dose	Up to 24 months after Disc of Trt date
Concomitant medications/proc edures			To be collected from the time of Screening visit through the Safety Follow-up visit										
Transfusion and growth factors			If administered, to be collected from the time of Screening visit through the Safety Follow-up visit										
Post-trial therapy data collection													x
Survival status													x
Secondary hematologic malignancy status													x

AE = adverse event; CA-125 = cancer antigen 15, CT = computed tomography; ctDNA = circulating tumor DNA; CXDX = Cycle X Day X, Disc of Trt = Discontinuation of treatment; ECG = electrocardiogram; ECOG = Eastern Cooperative Oncology Group; EOT = end of treatment; ICF = informed consent form; MRI = magnetic resonance imaging; NGS = next-generation sequencing; PCWG3 = Prostate Cancer Working Group 3; PE = physical examination; PK = pharmacokinetic; PSA = prostate-specific antigen; RECIST = Response Evaluation Criteria in Solid Tumors; SAE = serious adverse event; WOCBP = women of childbearing potential

- Screening:** Screening Period extends from Day -28 to Day -1. Screening laboratory assessments (hematology, chemistry, urinalysis, and serum tumor marker) may be used as Day 1 assessments if performed within 96 hours of the first dose of trial intervention. ECOG performance status and PE that are completed within 24 hours of first dose of trial treatment may be used as Day 1 assessments. Procedures that are to be performed as part of the practice of medicine and which would be done whether or not trial entry was contemplated, such as for diagnosis or treatment of a disease or medical condition, may be performed and the results subsequently used for determining trial eligibility without first obtaining consent. Participants must continue to meet eligibility criteria prior to the first dose of RP-3467 on Day 1.
- EOT Visit:** An End-of-Treatment visit will be conducted following the last dose of trial intervention and within +7 days from the discontinuation of treatment date. If a participant comes to the clinic to start a new cycle but the decision is made to discontinue treatment, that visit may be used as the EOT visit. The EOT visit should occur prior to the start of subsequent anticancer treatment.
- Safety Follow-up:** Required for all participants who discontinued from treatment for whatever reason. The window for the Safety Follow-up visit will be 30 (+14) days from the last dose of trial intervention.
